In addition to the 8 scripted messages, we will send an additional 8 unscripted role modeling messages, that describe strategies used by "positive deviants" to successfully adopt the key targeted behaviors. The intervention will be delivered over a 16-week period, which falls within the duration observed in previously published IYCF messaging interventions that demonstrated positive impacts.¹⁰ One voice and one text message will be sent each week over the 16-week period, which is aligned with both the previously published literature¹⁰ as well as the community preferences identified through our formative work.

We will not provide participants with phones as part of this intervention. Cell phone ownership is very high in these communities. In most cases, adults have their own phones. In the event that the man or woman participating in the study do not have their own phone, we will ask them if there is a phone that they have access to in the household. In this situation, we will send the voice messages to that phone. However, if they do not have access to a phone we will not continue the recruitment process. There will be no costs to the participants receiving the messages. We will cover all costs of sending the messages and the minutes spent sending them. Using a combination of voice and text messages will enable us to ensure that messages reach phones in areas with poor mobile coverage, while also accounting for literacy levels. Baseline and endline surveys will be conducted in both the control and experimental groups. The control group will receive the 16 messages after the completion of data collection.

Randomization of intervention: Computer-generated random numbers will be used to randomize 104 villages in a 1:1 allocation, stratified by village size (number of households per village) and region (Thiès, Diourbel, Fatick), to receive either the intervention (experimental group) or usual care (control group). Randomization will be conducted following a baseline survey and, given the nature of the intervention, will not be blinded. The intervention will be delivered over a 16-week period.

Data collection for process and economic evaluation:

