Considerations related to COVID-19: We do not anticipate engaging in any research activities until February 2022. Baseline data collection assessments for won't be conducted until May 2022 at the earliest. It is likely that the threat posed by the pandemic will be significantly lower at that time and a higher proportion of the Senegalese population will be vaccinated. However, given the uncertainty related to the COVID-19 pandemic, we are prepared to make modifications to our study protocol in order to protect human subjects. First, we will conduct all data collection outside. This is aligned with the data collection procedures that are typically used in these settings. Surveys are conducted outside of the home, in the household's private yard either sitting on a mat or in chairs. Given that the risk of virus transmission is incredibly low outside, we will ensure that all data collection is conducted outside, while maintaining the privacy of study participants. Second, enumerators will conduct the surveys at a six feet distance from the survey participants. This will allow us to maintain social distancing guidelines. While the enumerators conducting the household surveys will be able to maintain a six-foot distance between themselves and the study participants, this will not be possible for the anthropometric agent who will be testing hemoglobin levels using Hemocue machines. Third, if the risk of COVID-19 remains at the time of data collection, our enumerators will wear masks and gloves while conducting the surveys. Given the inability to maintain social distancing by the anthropometric agents, they may be provided with additional personal protective equipment (PPE) (e.g., N95 Masks) for their protection as well as the protection of study participants. Fifth, we will consult directly with the IRB at CNERS in Senegal to ensure that we are taking all the necessary precautions to protect both our enumerators but also our human subjects participants. Given that our intervention will be conducted on mobile phones, no adjustment to our intervention delivery would be required.

B. Data Points

We will collect data at baseline and endline. We will also collect process evaluation data after completing the endline data collection.

There is no long-term follow-up included in this study.

C. Study Duration

The total project duration is two years.

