1.9 Data Collection

A. Primary Data Collection

- **Location**: We will conduct cognitive testing of messages as well as household surveys (including hemoglobin measurements of infants and young children) outside of the homes of survey participants. In the local context of this study, households generally have a small dwelling and a surrounding yard/compound. Based on our team's previous experience working with these communities in Senegal, there is a preference for conducting surveys outside the home in the surrounding yard. This allows sufficient space while also allowing for privacy during the interviews.
- **Process of Data Collection**: We will work closely with a team of local enumerators from Senegal. We have previously worked with these enumerators in Senegal and they have extensive knowledge of the communities in which this study will take place. In addition to their previous experience working with these communities, the enumerators will be trained by the PI, supported by our local partners (Institut de Recherche en Santé de Surveillance Epidemiologique et de Formation) in Senegal; IRESSEF), to assist with data collection. Our local partners have experience working with the local enumerators and conducting similar work in these communities. The enumerators are not part of the research team but will be paid for their services, which is typical of research conducted in these settings.
- **Timing and Frequency**:

Cognitive testing: Participants included in the cognitive testing will only have one visit (~30-45 minutes) with the study team.

cRCT and process evaluation: Each participating household will have two visits from the study team. One visit for the baseline data collection and a second for the endline data collection. In addition, participants who will take part in the semi-structured interviews as part of the process evaluation, will have third study visits by our team.

In addition to the study visits to collect data, participants will receive voice and text messages to their cellular phones one time per week. Each message will be approximately 2 minutes in duration. The messages will continue for a period of sixteen weeks (total of 16 messages).

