6.0 Data Management Plan

6.1 Data Analysis

Cognitive testing: As mentioned previously, we will take detailed notes during the cognitive testing. The notes will be subsequently analyzed by members of the study team ([name] & [name]) by assessing common themes/patterns in the message comprehension. Summaries that describe the issues noted for each message and how they were addressed will then be prepared and discussed as a team, in an iterative way until the point of theoretical saturation.

cRCT: To estimate the impact of the mHealth messaging intervention on anemia and MAD, as well as our secondary outcomes, we will utilize a difference-in-differences approach. Linear regression models will be fitted for each outcome, with explanatory variables that include the intervention indicator, time (baseline and endline), and intervention by time interaction. The interaction term is of primary interest, as it summarizes mean changes in the outcome before and after the intervention in the treatment group compared with the control group. The intervention variable is as randomized (intention to treat). We anticipate that the parallel trend assumption will hold in this scenario since the various clusters and triads within clusters are similar to each other socio-economically; however, we will carefully test this assumption by applying the recently developed difference-in-difference model checklist⁴. We will analyze the data on the individual level and use generalized estimating equation (GEE) extensions of regression in SAS 9.4 to account for clustering. All models will adjust for sex of the child, socioeconomic status of the family and highest education completed by the mother. We will also conduct exploratory subgroup analyses based on baseline anemia status.

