Description of Statistical Approach: To estimate the impact of the mHealth messaging intervention on anemia and MAD, as well as our secondary outcomes, we will utilize a difference-in-differences approach. Linear regression models will be fitted for each outcome, with explanatory variables that include the intervention indicator, time (baseline and endline), and intervention by time interaction. The interaction term is of primary interest, as it summarizes mean changes in the outcome before and after the intervention in the treatment group compared with the control group. The intervention variable is as randomized (intention to treat). We anticipate that the parallel trend assumption will hold in this scenario since the various clusters and triads within clusters are similar to each other socio-economically; however, we will carefully test this assumption by applying the recently developed difference-in-difference model checklist⁴. We will analyze the data on the individual level and use generalized estimating equation (GEE) extensions of regression in SAS 9.4 to account for clustering. All models will adjust for sex of the child, and highest education completed by the mother. We will also conduct exploratory subgroup analyses based on baseline anemia status.

References

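### The two-wave difference-in-differences is unbiased under randomisation but less precise than an endline analysis adjusted for the baseline outcome; its covariates add almost nothing, and one pre-intervention wave cannot show a pre-trend

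*SAP*

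**What the plan says.** The SAP (Description of Statistical Approach) and protocol section 6.1 specify the same estimator. Each outcome gets a linear regression "with explanatory variables that include the intervention indicator, time (baseline and endline), and intervention by time interaction", fitted by GEE to allow for clustering, and the interaction is the effect of interest. The arm main effect is free and the baseline outcome is not a covariate.

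On design, protocol section 1.3 states: "Randomization will be conducted following a baseline survey and, given the nature of the intervention, will not be blinded". It also states: "We will collect data at baseline and endline". Section 1.9 adds: "Each participating household will have two visits from the study team". There is thus one wave before the intervention and one after, in the same households, and section 1.9 says no secondary data will be used.

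On covariates the two documents differ. The SAP has: "All models will adjust for sex of the child, and highest education completed by the mother". Protocol section 6.1 has: "All models will adjust for sex of the child, socioeconomic status of the family and highest education completed by the mother".

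The SAP expects parallel trends to hold because "the various clusters and triads within clusters are similar to each other socio-economically", and then says "we will carefully test this assumption by applying the recently developed difference-in-difference model checklist". The checklist is cited as reference 4. The SAP's list stops at reference 1, and reference 4 in the protocol is a report on investment in nutrition in Senegal.

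**The concern.** When allocation is random and follows the baseline survey, the arms differ at baseline only by chance. DiD subtracts that chance difference in full. Adjusting for the baseline outcome subtracts only the part that predicts endline, so it leaves less noise. The trial already collects the baseline outcome on every child, so leaving it out of the model gives up precision on both primary outcomes for no saving.

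The covariates that are planned cannot make up for this. A variable that is fixed over 16 weeks and enters without a time interaction drops out of a within-child change.

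The parallel-trends text rests the comparison on the wrong support. Randomisation justifies it; socio-economic similarity is not needed. Promising to test the assumption, when no pre-trend can be observed, invites argument over a comparison the design already supports.

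**Working it through.** **Inputs** (protocol section 1.5): two-sided α of 0.05; 102 clusters of 5 triads, so 51 per arm; ICC 0.02; 5% attrition; anaemia 66% with a 6-point difference; MAD 46.8% with a 7-point difference. I take the effects as 66% to 60% and 46.8% to 53.8%. The within-child correlation ρ is not in the documents and is shown as a range.

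**The plan's own power figures.** Children per arm at endline: 51 × 4.75 = 242.25. Design effect: 1 + 3.75 × 0.02 = 1.075. Effective number: 242.25 / 1.075 = 225.3 per arm.
- Anaemia: variance (0.66 × 0.34 + 0.60 × 0.40) / 225.3 = 0.00206, SE 0.0454, power 26% (stated 81.7%).
- MAD: variance (0.468 × 0.532 + 0.538 × 0.462) / 225.3 = 0.00221, SE 0.0470, power 32% (stated 88.8%).

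An endline comparison therefore does not reproduce the stated figures. A DiD variance comes close only with an unstated ρ of about 0.89, which gives 80.5% and 88.8%. That discrepancy is a separate problem. It matters here because 0.89 is the only value of ρ that the documents imply, even indirectly.

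**Variance factors**, relative to an unadjusted endline comparison:
- DiD: 2(1 − ρ)
- Endline adjusted for baseline: 1 − ρ² = (1 − ρ)(1 + ρ)
- Ratio, adjusted to DiD: (1 + ρ)/2, below 1 for every ρ below 1
- DiD exceeds 1, and so is worse than endline alone, when ρ is below 0.5

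| ρ | DiD factor | Adjusted factor | Ratio | Anaemia power, DiD → adjusted | MAD power, DiD → adjusted |
|---|---|---|---|---|---|
| 0.3 | 1.40 | 0.91 | 0.65 | 20% → 28% | 24% → 34% |
| 0.5 | 1.00 | 0.75 | 0.75 | 26% → 33% | 32% → 40% |
| 0.7 | 0.60 | 0.51 | 0.85 | 40% → 46% | 48% → 55% |
| 0.89 | 0.22 | 0.208 | 0.945 | 80.5% → 82.6% | 88.8% → 90.4% |

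**Simulation with binary clustered outcomes** (104 villages of 5, stable village effect, 5% attrition, no true effect, 66% prevalence, 8,000 runs per setting). The adjusted-to-DiD variance ratio was 0.64, 0.68, 0.77, 0.83, 0.89 and 0.94 at within-child correlations of 0.22, 0.32, 0.48, 0.64, 0.76 and 0.87. These gains are slightly smaller than the formula gives. In sample-size terms they run from 1/0.64 − 1 = 56% more children down to 1/0.94 − 1 = 6%. At 46.8% prevalence the ratios were 0.65, 0.69, 0.77 and 0.89 at correlations of 0.23, 0.33, 0.49 and 0.76. Both estimators averaged zero. Endline alone had 0.69 and 0.78 of the DiD variance at correlations of 0.22 and 0.32, and 1.04 at 0.48.

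**Covariates.** In 300 simulated panels, adding fixed sex, education and socioeconomic status left the interaction and its SE identical when every child had both waves. With 5% attrition the interaction moved by 0.0016 on average and the SE ratio was 0.999; with 10%, 0.0023 and 0.999.

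**Strata.** Region and village size could remove at most the between-village part of the variance. For an unadjusted endline comparison with 5 children per village and ICC 0.02 that is 1 − 0.98/1.08 = 9%. It would be less after baseline adjustment, and is probably near zero.

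**Pre-trend.** A pre-trend needs at least two waves before the intervention. The plan has one, and no outside data.

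**The case against.** DiD is valid, targets the intention-to-treat effect, and is prespecified consistently in the protocol and the SAP, so replacing it is an improvement rather than the correction of an error. The size of the gain depends on a correlation nobody has reported, and at the one value the documents imply, about 0.89, it is roughly two points of power. At moderate ρ neither estimator approaches 80%, so the low absolute powers reflect the sample-size section and not the choice of estimator. Using one design effect for both estimators is also a simplification: a stable village effect cancels from DiD. Socioeconomic status measured at each wave would not cancel, and the household survey is run at both. Finally, the SAP never names a pre-trend test, and its checklist may contain items that two waves allow.

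Most of this stands as qualification. The conclusion is about precision only, and the variance ratios carry it better than the power pairs. The simulation, which does use a stable village effect, gives nearly the same ratios as the formula. The value 0.89 is solved from stated power and is not evidence about the children. For MAD there is reason to expect less: it is a yes/no threshold from a one-day recall, its meal-frequency cut-off changes at 9 months of age, and the waves run from May/June to October. None of these points makes DiD as precise as the adjusted analysis at any ρ below 1.

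**Conclusion.** The point holds. The planned DiD is unbiased given randomisation and non-informative attrition, but it is less precise than an endline analysis adjusted for the baseline outcome. The adjusted analysis has about 65% of the DiD variance at ρ = 0.3, 75% at 0.5, 85% at 0.7 and 94.5% at 0.89. The gain is therefore large if ρ is low or moderate and small if it is near 0.9. Below about 0.5, DiD is also less precise than ignoring baseline altogether. Baseline adjustment does not restore 80% power at moderate ρ.

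The planned adjustment for sex and education does no harm and adds essentially nothing. Socioeconomic status appears in the protocol model but not in the SAP model, whichever estimator is used. A pre-trend test cannot be run; other checklist items cannot be judged, because the checklist is not in the documents. The change should be made, with medium confidence because ρ is unknown.

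**What to change.** The right step depends on whether arm-level outcome results had been seen by the SAP date, 05/21/24. Endline was planned for October 2022 and allocation is unblinded, and the documents do not settle this.

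- **If results were unseen:** make the primary analysis a village-clustered GEE of the endline outcome on arm, adjusted for the baseline outcome, region and village-size stratum (as design variables), baseline child age, sex, maternal education and baseline socioeconomic status. An equivalent two-wave model with a common baseline mean, that is, without the arm main effect, would keep children who miss one wave. Report DiD as a sensitivity analysis.
- **If results had been seen:** keep DiD as the named primary analysis, report the baseline-adjusted model as a labelled sensitivity analysis, and disclose the timing.
- **In both cases:** replace the parallel-trends test with a statement that randomisation supports the comparison, and report baseline balance and attrition by arm. If the checklist is kept, give its reference and name the items that two waves allow. Reconcile the covariate lists, and say whether socioeconomic status is the baseline or a wave-specific value.

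The cost is SAP wording and a few lines of SAS, using data already planned for collection. There are two small downsides: the prespecified estimator is changed or supplemented, and the plain endline model needs an observed baseline outcome.

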cRCT sample. The villages in which we are conducting this study are subsistence farming communities with high levels of poverty and malnutrition in three regions of Senegal: Thies, Diourbel and Fatick. Each of the 104 villages that will be included in the study have been purposively selected to ensure that they have an established farming group, and that they are sufficiently geographically dispersed in order to minimize risk of contamination. We will use the list of the household members of the farming groups of each of the 104 villages included in the cRCT as our sampling frame. Based on [name] previous experience, we will identify all households within the farming group that have a child 6-19 months of age at baseline (to ensure that the child is not >23 months at endline), and we will subsequently randomly select five mother, father and child triads to be included in our study sample. In some cases, the primary caregiver of the child may be a close relative rather than the birth mother. In these instances, the primary caregiver will receive the voice and text messages along with her husband or primary male caregiver. In total, we will sample 510 triads in 104 villages (~5 households/triads per village). Thus, our sample will include 510 mother, father and child triads. Baseline data collection will take place in May/Jun 2022, the intervention will be delivered between Jun-Sep 2022 and the endline data collection will take place in October 2022.

Process Evaluation sample: A smaller purposive sample of approximately 45 mothers and fathers, implementation project staff and CHWs will be included in Aim 2 of the project as part of the in-depth semi-structured interviews and focus groups conducted in the process evaluation. We will purposively select three villages from each region (n total = 9 villages) in order to maximize variation in village characteristics such as size, distance to urban settings, distance to markets, etc. Interviewees and focus group participants will be purposively selected from the list of all mothers and fathers receiving the voice messages in each of these villages to ensure variation in participant socio-demographics (e.g., household size, parity, age, etc.) as well as key people involved in the intervention's implementation. The process evaluation data collection will take place in between October and December 2022.

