participation, we will ask the household head if there is a child 6 to 19 months in the household. If there is more than one child between 6-19 months, we will select the youngest child to participate in the study. We will then confirm the child's age using a vaccination card or birth certificate. We will also ascertain the age of the mother and father to ensure that they are 18 years of age or older.

Process evaluation: After the completion of the endline survey, enumerators will ask participants if they would be willing to participate in a semi-structured interview as part of the process evaluation. Of those that indicate their willingness to participate, we will purposively select participants in order to ensure that we include variation in terms of the socio-demographic characteristics of participants.

- **Exclusion Criteria**

Exclusion criteria include parents of children over the age of 24 months, those without access to a mobile phone and those that are cognitively impaired.

D. Privacy Protections

We do not anticipate any risks to participants or their privacy in the recruitment process. Furthermore, the recruitment process will be completed one-on-one with the participants such that their decision to participate or not will be theirs alone and any questions or concerns they have about the project will not be shared. The mother and father being recruited in the study will be recruited separately in the household compound. The enumerator will explain the study to both the parents together but will then take each potential participant aside in order to obtain consent. One enumerator will visit each household. If the layout of the household compound (which normally includes huts within a fenced off area of the compound) does not permit privacy from other family members, the enumerator will take the potential participant outside of the household compound in order to obtain consent.

We have previously worked in these study communities and have not had any problems in terms of the gender of the enumerators in terms of conducting surveys. We do not anticipate any problems in terms of allowing women to be alone with enumerators if they are male.

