Study Title: The Impact and Implementation of a Mobile Messaging Intervention to Improve Infant and Young Child Nutrition in Senegal

NCT Number: NCT05374837

Document date: 05/21/24

Document name: Statistical Analysis Plan

STATISTICAL ANALYSIS PLAN

Study outcomes: Table 1 provides an overview of our study outcomes.

Table 1. Overview of study outcomes

Outcome type	Outcome	Description
Primary	Anemia prevalence	We will use Hemocue Hb301 machines to measure hemoglobin levels in children in order to determine anemia prevalence using the WHO cut-offs: mild $10 \leq \text{hb} < 11 \text{ g/dl}$; moderate $7 \leq \text{hb} < 10 \text{ g/dl}$ and severe $\text{hb} < 7 \text{ g/dl}$. A finger prick will be used to obtain a drop of capillary blood that is placed on a cuvette and inserted in the Hemocue machine to obtain an on-the-spot assessment of hemoglobin levels.
	Minimum Acceptable Diet	Minimum Acceptable Diet Prevalence, Primary, baseline and endline: The minimum acceptable diet indicator will be used to assess dietary diversity in children. A 24-hour open dietary recall will be conducted with mothers to assess their child's dietary intake over the previous day. The 24-hour recall will be used to calculate minimum dietary diversity (MDD) (consuming ≥ 4 of 7 food groups (grains, roots and tubers; legumes and nuts; dairy products; flesh foods; eggs; vitamin A rich fruits and vegetables; other fruit and vegetables)) and minimum meal frequency (MMF) (2x/day for breastfed infants 6-8.9 months; 3x/day for breastfed children 9-23.9 months; 4x/day for non-breastfed children 6-23.9 months). Children who meet the thresholds for both MDD and MFF are defined as consuming a MAD, based on the WHO/UNICEF IYCF indicator.
Secondary	Frequency of consuming key foods in past 7 days	Frequency of consuming key foods in the past 7 days, Secondary, baseline and endline: We will use a 7-day food frequency questionnaire (FFQ) to assess the frequency that children consumed specific foods targeted in the intervention over the course of the previous week. More specifically, the FFQ will ascertain the number of times that the following foods have been consumed: eggs, leafy greens, fish, milk, cowpea, nuts, orange colored fruits and vegetables, other fruits and vegetables, thick porridge, beef or mutton, pork, chicken and liver.

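### The MAD meal cut-off rises between surveys for breastfed children aged 6-8.9 months at baseline, and the planned MAD model has no age-by-time term to remove the resulting noise

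*SAP*

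**What the plan says.** **Outcome.** SAP Table 1 (and protocol 1.6 B, Table 1) counts a child as meeting MAD if both the food-group and the meal-frequency thresholds are met. The meal thresholds are "2x/day for breastfed infants 6-8.9 months; 3x/day for breastfed children 9-23.9 months; 4x/day for non-breastfed children 6-23.9 months".

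**Timing.** Under protocol 1.3, eligible households "have a child 6-19 months of age at baseline". "Baseline data collection will take place in May/Jun 2022", and "endline data collection will take place in October 2022". Protocol 1.9 has the same households visited on both occasions. Between the visits, "The intervention will be delivered over a 16-week period".

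**Model.** The SAP (Description of Statistical Approach) fits a linear model with arm, time and arm by time, using GEE for clustering. On covariates it says: "All models will adjust for sex of the child, and highest education completed by the mother". Protocol 6.1 has the same model and also lists socioeconomic status. Child age is on neither list. Randomisation (protocol 1.3) is stratified by village size and region, not by age.

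**Age data.** Protocol 4.1 C states: "We will then confirm the child's age using a vaccination card or birth certificate".

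**The concern.** A child's MAD status can change between surveys because feeding changed or because the standard rose. For breastfed children aged 6-8.9 months at baseline, the standard always rises. For children aged 9 months or more it does not rise on account of age; it moves from 3 to 4 only if the child is weaned between surveys. The average change in MAD may therefore differ between the two age groups for a reason unrelated to the messages.

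The primary estimate compares mean changes between arms. If one arm happens to contain more of the youngest children, part of this age-specific change enters the estimate. Age is not a stratification factor, so nothing in the design limits the imbalance. The listed covariates are fixed over time and enter as main effects, so the model does not remove it either. What is at stake is a little precision on one of the two primary outcomes, which could be recovered from a value the trial already holds.

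**Working it through.** The plan gives no figure for this effect. Its nearest one, 88.8% power for a 7-point MAD difference (protocol 1.5), does not follow from the listed inputs: 255 × 0.95 / 1.08 = 224 effective children per arm, 46.8% v 53.8%, two-sided 0.05, gives 31.6%. That is a separate matter, and nothing below depends on it.

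**1. Does every child in the band cross 9 months?** The shortest gap the calendar allows is 30 June to 1 October: 93 days, and 93 / 30.44 = 3.06 months. A child aged exactly 6.0 months at baseline is then 9.06 months at endline. A 16-week gap (112 days, 3.68 months) gives 9.68 months. So the whole band crosses. The cut-off goes from 2 to 3 for those still breastfed and from 2 to 4 for those weaned.

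**2. How many children?** The documents give no age distribution. If ages are uniform (assumption), the band is 3/14 = 21% to 3/13 = 23% of the sample. This is an upper figure for the breastfed group, since a non-breastfed infant faces 4 meals at both surveys.

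**3. How does it enter the estimate?** Let q be the share of an arm in the youngest band, and D_y and D_o the mean changes in MAD for younger and older children, messages aside. Then

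interaction = effect + (q_int − q_ctl) × (D_y − D_o) + other sampling error.

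Under randomisation the second term has mean zero. The average step, q × D_y, is common to both arms and goes into the time term.

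**4. How large is that term?** With 255 × 0.95 = 242 children per arm and clustering ignored, SD(q_int − q_ctl) = √(2 × 0.214 × 0.786 / 242) = 0.037. The documents give no MAD change by age, so the contrast D_y − D_o is assumed:

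- −15 v +5 points, a contrast of 20: SD = 0.037 × 20 ≈ 0.75 points
- −25 v +10 points, a contrast of 35: SD = 0.037 × 35 ≈ 1.3 points

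Simulated standard errors of the interaction for these cases (3,000 runs, moderate within-child correlation, clustering ignored) are 5.57 and 5.53 points. The age term's share of variance is (0.75 / 5.57)² ≈ 2% and (1.3 / 5.53)² ≈ 6%.

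**5. Does an age-band-by-time term recover it?** In those simulations the SE falls from 5.57 to 5.54 (variance down about 1%) and from 5.53 to 5.36 (about 6%). A second simulation (1,500 runs per setting, true effect 7 points, uniform ages, drop in the youngest band only) gives:

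| Assumed drop (points) | SD, planned model | SD, band × time added | Variance change |
|---|---|---|---|
| 0 | 0.0614 | 0.0614 | 0% |
| 10 | 0.0619 | 0.0620 | about 0% |
| 20 | 0.0635 | 0.0630 | −1.6% |
| 30 | 0.0622 | 0.0613 | −2.9% |
| 40 | 0.0619 | 0.0597 | −7.0% |

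The mean estimate is 0.068 to 0.072 under both models, which confirms that no bias is being removed.

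**6. Would a plain age covariate do?** No. With complete pairs, a time-constant main effect leaves the arm-by-time coefficient unchanged; the largest difference in simulation was 4 × 10⁻¹⁵. The product with time is what does the work.

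**The case against.** The strongest objection is that this is too small to matter. Using the simulated standard errors, two-sided power for 7 points moves from 24.1% to 24.3% in the milder case and from 24.4% to 25.7% in the stronger one. Leaving one mildly prognostic covariate out of a randomised comparison is usually a matter of preference. That stands, and it is why the point ranks low.

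The size also rests on assumptions. The documents give one overall MAD prevalence, 46.8%, and nothing by age. MAD also requires at least 4 of 7 food groups, so a rise in the meal cut-off lowers MAD only among infants who had met both criteria and then miss the extra meal. If few do, the gain is near zero. This stands too, and the range given here starts at zero.

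An age-specific standard is the indicator's intended design. That is correct: the definition is not at fault and should not be changed. The point concerns only how the model handles it.

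Finally, adding terms has a cost. The SAP is dated 05/21/24, the planned endline was October 2022, and the trial is not blinded. A change to the primary model after outcome data by arm have been seen would be post hoc. The documents do not say whether they have been seen, so the remedy is conditional on that.

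Three stronger readings are tempting, and the documents do not support them. A reader might infer that the rising cut-off biases the treatment effect; it applies equally to both randomised arms, and the time term absorbs its average. A reader might set the 0.75 to 1.3 points against the 7-point target as an extra error; it is one component of a standard error of about 5.5 points and is already counted there. A reader might extend the argument to anemia; the hemoglobin cut-offs in SAP Table 1 do not vary with age over this range.

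**Conclusion.** The point holds as a minor matter of precision in the MAD analysis. From the documents alone, every breastfed child aged 6-8.9 months at baseline faces a higher meal cut-off at endline, and neither covariate list nor the stratification deals with it. The consequence is avoidable noise. Removing it lowers the variance of the arm-by-time estimate by about 0 to 6% for contrasts of 0 to 35 points between the age groups, and by about 7% at 40 points.

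These percentages assume uniform ages from 6 to 19 months, about 242 children per arm, independent children and the age-specific MAD changes shown above. The crossing of 9 months needs none of these; it follows from the planned survey dates and the definition.

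**What to change.** In the MAD model only, add baseline age band (6-8.9 months v 9 months or more, the break used in the MAD definition) and its product with time. Both terms are needed. Age at baseline is collected before randomisation, so adjusting for it is safe. Make the same addition to the covariate lists in the SAP (Description of Statistical Approach) and protocol 6.1, and settle at the same time whether socioeconomic status belongs in both.

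If outcome data by arm have already been seen, keep the planned model as primary and report the extended model as a labelled sensitivity analysis.

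The cost is one sentence in each document and two model terms, with no new data. The loss of degrees of freedom is negligible with about 500 children in 104 villages.
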